## 7.2.2 OTHER ASSAYS OR PROCEDURES

N/A

## 7.2.3 SPECIMEN PREPARATION, HANDLING, AND STORAGE

At baseline and on day 1-3 and 30 after TBI, the blood/saliva samples will be collected. About 8cc of blood will collected and after clotting, the sample will be centrifuged at 4 degrees Celsius for 10 minutes at 1300g. The blood will be centrifuged within 1 hour of collection. The plasma and saliva will be collected and aliquoted into 1 ml cryovial tubes and immediately frozen at -80 degrees Celsius. Information pertaining to each sample will be added to the specimen log. All personnel will be trained in accordance to the CDE recommendations.

## 7.2.4 SPECIMEN SHIPMENT

For the biochemistry, we will schedule the Quest Diagnostics courier to collect the samples at UTSWMC to deliver the blood samples to Quest Diagnostics for analysis.

## 7.3 STUDY SCHEDULE

## 7.3.1 SCREENING

Boxers that meet the baseline study criteria will be approached and if interested they will be consented to participate in the study procedures. Medical and concussion history will be reviewed at the baseline time-point to determine which boxers will be considered to participate in the study. The research coordinator/boxing consultant will identify the athletes that have experienced greater than 25 blows to the head or a Symptom Score > 1 on at least 3 items from the Rivermead Post-Concussion Questionnaire following the boxing match. Once the subject has been identified, the research personnel will review the subject's chart to determine if they meet criteria for enrollment into the study. If so, the participant will be approached to obtain consent where the patient has the right to ask questions about the study.

## 7.3.2 ENROLLMENT/BASELINE/FOLLOW-UP

#### Sildenafil Study:

#### Baseline Visit (Visit 1, Day 0)

- Obtain informed consent of potential participant verified by signature on study informed consent form
- Verify inclusion/exclusion criteria
- Obtain demographic information, medical history, head injury history, medication history, alcohol and tobacco use history
- Record vital signs, results of examinations, other assessments.
- Baseline symptom questionnaire
- Collect blood/saliva for biochemistry, biomarker testing
- MRI procedures
- Neuropsychological testing
- •

## Follow-up Visit (Visit 2, 2 hours after injury)

• Administer sildenafil (60mg) or placebo once of daily for 14 days

#### Follow-up Visit (Visit 3, Day 1-3)

- Record adverse events
- Collect blood/saliva for biochemistry, biomarker testing
- Administer sildenafil or placebo (once)
- MRI procedures
- Neuropsychological testing

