The participants in **group 1** (single therapy) will consist of the active boxers/MMA fighters that experience significant sub-concussive blows or a concussion during competition. In this group, 65, professional male/female boxers/MMA fighters within the North Texas region will be screened and about 50 concussed athletes will be enrolled. The athletes that have at least 25 blows to the head and a Symptom Score > 1 on at least 3 items from the Rivermead Post-Concussion Questionnaire following their fight will be enrolled in this study. The research subjects will be treated with sildenafil (60mg), once at 2 hours after experiencing a concussion.

**Group 2** will consist of the active boxers/MMA fighters that experience significant subconcussive blows or a concussion during competition. In this group, 65, professional male/female boxers/MMA fighters within the North Texas region will be screened and about 50 concussed athletes will be enrolled. The athletes that have at least 25 blows to the head and a Symptom Score > 1 on at least 3 items from the Rivermead Post-Concussion Questionnaire following their fight will be enrolled in this study. Once enrolled, the subjects will be treated with sildenafil (60mg) once-a-day for 14 days.

**Healthy Control group:** In this study, 80, age (between 18 and 35)-matched healthy controls will be enrolled. The control subjects will participate in neuropsychological testing, blood/saliva collection, and the MR imaging procedures. Healthy controls will be tested in group 1 (n=40) and 2 (n=40) and randomized to receive either sildenafil or placebo in this group.

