#### The BOLD sequence with hypercapnia challenge:

The participants will have a BOLD MRI scan (baseline, day 1-3, and 30 after injury) with CVR hypercapnia measurements. Global and region-specific CVR will be assessed using hypercapnia induced by breathing 5% carbon dioxide (CO2) mixed with 21% O2 and 74% N2. Study participants will be taken out of the scanner after the initial 45-minute structural scan and fitted with a breathing mask that covers the mouth and nose (similar to a C-PAP mask). After

the mask is in place, the patient is placed back into the magnet. Hypercapnia will be induced via a Douglas bag fitted with a valve to switch between room air and 5% CO2. A research assistant will be inside the magnet room throughout the BOLD scan with hypercapnia challenge to switch the valve and monitor the subject. Physiologic parameters, including end-tidal (EtCO2), breathing rate, heart rate, and capillary oxygenation will be monitored continuously during the experiment using a capnograph and pulse oximeter. The type of gas breathed is switched every minute similar to a block design fMRI experiment, while Blood Oxygen Level Dependent (BOLD) MRI Images are acquired for 7 minutes.

Times are close approximations which may be altered depending on the cooperation of the patient. The subject will not engage in the hypercapnia challenge for more than the specified 7 min. Total scan time with structural and BOLD sequences will be approximately 1 hour.

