# 6.1.5 DOSING AND ADMINISTRATION

STU032018-063, [name], FormA-ResearchProtocol, Mod\_6, 11-25-19 (1) NIH-FDA Clinical Trial Protocol

In the first and second group, the participants will be administered either a single-dose or 14 pills of placebo or sildenafil (60mg) after suffering a concussion. The first dose will be taken at 2hours after injury.

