#### **Trial Safety**

Throughout the study, the study coordinator and investigators will monitor the participants for AEs. The study coordinator will contact the study participants every 7 days to monitor for adverse events. To monitor for drug toxicity, at the 2nd visit to UT Southwestern Medical Center (day 1-3), 8cc of blood will be collected to determine toxicology, liver function, and coagulation after taking the study drug (sildenafil) for 1-3 days. The study participants will be asked to notify the study team if planning to take any other drug besides the study drug. The participants will also be asked to maintain a daily log of medications taken other than the study drug to monitor drug to drug interactions.

Safety oversight will be under the direction of study PI, medical monitors (Drs. [name] and [name]) and the research coordinator. A written reported will be submitted to the DSMP members every 6 months. The ISMs will only meet to discuss reported AEs. Events determined by the PI and co-investigators to be unexpected adverse events involving risks to subjects or others will be reported by the contact PI to the IRB and FDA within 7 business days. With respect to unexpected adverse events, the contact PI will inform the ISMs within 24 hours of this occurrence and will provide the ISMs with AE listing reports. The ISMs will convene an ad hoc meeting by teleconference or in person as soon as possible and provide recommendations for proceeding with the study to the study sponsor and IRB. The ISM will provide its input in the report to the PI and IRB. The contact PI will inform the FDA if there is a temporary or permanent halt of the study. All study members will be informed by the contact PI about any unexpected adverse events.

Upon the reporting of unexpected adverse events a participant, the study coordinator will collect a blood sample (8cc) to determine blood chemistry and will conduct follow up medical monitoring. The Quest Diagnostics laboratory (Dallas, Texas) will perform the biochemical tests. The subject information, adverse event report (if any), and research chart will be kept in a locked file cabinet in the research office (South Campus H7.126). Only study investigators and coordinators will have access to the subject's file.

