## 10 STATISTICAL CONSIDERATIONS

#### 10.1 STATISTICAL AND ANALYTICAL PLANS

#### STATISTICAL ANALYSIS PLAN

#### Study design and randomization scheme

Once eligibility is confirmed, based upon defined inclusion and exclusion criteria, randomization will occur within 2 hours of a bout. The placebo-controlled double-blind design will diminish concern about predictability of treatment assignments. The unblinded study biostatistician will prepare a randomization schedule. Randomization will be 1:1 sildenafil:placebo, and will be in blocks of 2. Treatment allocation will be determined via a computer program that automatically generates random digits. Investigators associated with this study will not have access to the randomization schedule. The randomization program will also record the assignments to the corresponding boxers in the database and will display the assignments on the screen for action by the study coordinators.

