Also, we will assess the treatment effect of sildenafil on post-concussive symptoms and cognitive performance using two-sample t-test similarly as in the primary aim, but with the secondary endpoints of symptoms. On day 1 and 30 after injury we will then calculate the difference in CBF/CVR and each of the post-concussive symptom assessments and cognitive assessments after the single treatment of sildenafil. Also, we will assess the post-concussion correlations of CBF/CVR and cognitive performance by calculating the cross-sectional Pearson correlations of CBF/CVR with symptom inventory and neuropsychological CDEs collected at Day 1 and 30 after TBI. Correlations will be calculated separately and jointly at each time point, and for each of the subdomains of neuropsychological CDEs. Multiple comparisons will be adjusted by controlling the false discovery rate (FDR).

Our secondary analyses will consist of assessing the treatment effect of sildenafil therapy on brain biomarker levels using two-sample t testing, but with the secondary endpoints of symptoms. We will then calculate the difference in brain biomarker levels at the beginning of the sildenafil therapy and after the treatment period (Day 30 vs Day 1-3). Scatter plots including both arms will be generated based on the calculated differences and two linear regression models with changes in brain biomarkers as outcomes, and changes in symptoms as independent variables will be fit to assess the association between the recovery of the TBI-related markers. Potential confounders such as gender and treatment arm indicator will be adjusted in the model.

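### The Day 1-3 visit lists a study pill without naming a group, and no rule ties the Day 1-3 CBF/CVR scan to the last pill, so that scan has no defined drug state

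*Combined protocol and SAP*

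**What the plan says.** **Dosing.** Section 4.1 says of group 1: "The research subjects will be treated with sildenafil (60mg), once at 2 hours after experiencing a concussion". Group 2 takes one pill daily for 14 days. Section 6.1.5 covers both groups: "The first dose will be taken at 2hours after injury". Visit 2 in section 7.3.2, two hours after injury, reads "Administer sildenafil (60mg) or placebo once of daily for 14 days". The SAP (section 10.1, study design and randomization scheme) agrees: "randomization will occur within 2 hours of a bout". Section 9 (Trial Safety) has the Day 1-3 blood draw check "liver function, and coagulation after taking the study drug (sildenafil) for 1-3 days".

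Visit 3 (Day 1-3) in section 7.3.2 then lists "Administer sildenafil or placebo (once", above the MRI and neuropsychological items and without naming a group. The procedures table in section 7.1.1 marks randomization and dispensing only in its Day 1-3 column.

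**Scanning.** Section 4.2.1.a says "The participants will have a BOLD MRI scan (baseline, day 1-3, and 30 after injury) with CVR hypercapnia measurements" and allows a 3-day scheduling window. ASL, which gives resting CBF, is part of the roughly 45-minute structural block. BOLD with hypercapnia, which gives CVR, follows it. Section 6.1.9 asks participants to note in a diary when they took the drug. No section links pill time to scan time or uses the diary times in an analysis.

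**The concern.** CBF/CVR is a primary endpoint (sections 4.2.1 and 10.1), and Day 1-3 is one of its two post-injury measurements. Two things are unsettled there.

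The first is who takes a pill at that visit. A coordinator working down the Visit 3 list would give one to everyone. That would break the single-dose regimen, one of the two regimens under test.

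The second is what the scan measures. Section 2.1 cites a study in which CVR had risen by 1 hour after a dose, which is an acute effect. Sections 2.2 and 3 aim at less secondary injury and better outcomes after treatment, which is a lasting effect. A scan soon after a pill and a scan a day or more after it address different questions. The plan does not say which one the Day 1-3 value answers.

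**Working it through.** The plan states no figure on this point, so the check is a comparison of texts and simple interval arithmetic.

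**Step 1: dosing texts side by side.**

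| Place | When treatment starts | What it implies for a Day 1-3 pill |
|---|---|---|
| 4.1, groups 1 and 2 | Group 1: 2 h after injury; group 2: once enrolled | Group 1: none; group 2: that day's pill |
| 6.1.5 | First pill at 2 h | Supply is one dose or 14 pills |
| 7.3.2, Visit 2 | 2 h | Single pill, or daily for 14 days |
| 10.1, randomization scheme | Randomized within 2 h of the bout | Not stated |
| 9, Trial Safety | Before Day 1-3 | Participants already 1-3 days on drug |
| 7.1.1, table | Randomization and dispensing at Day 1-3 | Drug first handed out at this visit |
| 7.3.2, Visit 3 | Not stated | One pill, no group named |

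The first five rows agree with each other. The last two do not fit them. The table has no 2-hour column, so its entries may simply have been placed under the nearest heading. Visit 3 has no such explanation, because section 7.3.2 lists the 2-hour visit separately, just above it.

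**Step 2: time from last pill to the Day 1-3 scan.** Assumption: Day n means 24n hours after injury.

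- Group 1, 2-hour pill only: 24 - 2 = 22 h at Day 1 and 72 - 2 = 70 h at Day 3. If the 3-day window is added after Day 3, 70 + 72 = 142 h. The documents do not say whether the window is additional.
- 14-day group, one pill a day at no fixed clock time: about 0 to 24 h.
- If a pill is taken just before the scan starts (assumption; the order of the Visit 3 list suggests this but does not require it): ASL falls within about the first 45 minutes and BOLD at about 45 to 60 minutes, given a total scan time of about 1 hour. The two sequences are then at different times from the pill.

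**Step 3: Day 30.** With the first pill at 2 h, the 14th daily pill falls at 2 + 13 × 24 = 314 h. Day 30 is 720 h, so the gap is 720 - 314 = 406 h, about 17 days. Day 30 is off drug in both groups, so the ambiguity is confined to Day 1-3.

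**Step 4: what a result could mean.** The 14-day group's 0 to 24 h range includes the 1-hour point at which section 2.1 cites a CVR increase, and also times most of a day later. The documents give no duration of action. A null at Day 1-3 could therefore mean no acute effect, or an acute effect that had passed with nothing residual. A positive result shows an effect of assignment but does not say which kind.

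**The case against.** The strongest reply is that the Visit 3 line is only loose wording. Section 6.1.5 gives each participant one dose or 14 pills, the pharmacy packages the drug, participants take it themselves from bottles, and leftover pills are counted. Every other statement of the regimens is consistent. The natural reading is that Visit 3 refers to that day's pill in the 14-day group. This stands as the probable intent, but the text does not say so, and a visit checklist is what site staff follow.

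Four stronger readings might be inferred, and the documents do not support them:

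- That group 1 should be expected to take 120 mg (2 × 60) and group 2 900 mg (15 × 60). Both need a pill beyond the supply described in section 6.1.5, and no section provides one.
- That the synopsis shows the trial was built on an acute effect. It reports that sildenafil potentiates reactivity in chronic TBI but gives no timing. Only the single study cited in section 2.1 does. For group 1, a scan a day or more after one pill is a coherent test of residual effect.
- That the analysis treats Day 1-3 as pre-treatment. The SAP's secondary analysis does take "the difference in brain biomarker levels at the beginning of the sildenafil therapy and after the treatment period (Day 30 vs Day 1-3", but that concerns biomarkers and may loosely mean early in the 14-day course.
- That the comparison of arms is biased. The same rules apply to sildenafil and placebo.

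It is also fair that a 0 to 24 h range is inherent in once-daily dosing. That explains the range. It does not tell the reader which part of it the endpoint is meant to represent.

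Which visit CBF/CVR change is measured from, and whether results are reported by regimen, are separate questions not settled by a pill-timing rule.

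**Conclusion.** The point holds as a conflict of texts plus a missing rule. The Visit 3 item and the procedures table do not agree with the sections that start treatment within about 2 hours of injury and give group 1 one pill. Nothing sets the time from last pill to the Day 1-3 scan: about 0 to 24 h in the 14-day group, and about 22 to 70 h in group 1 under the 2-hour text if Day n means 24n hours.

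The consequence is limited to interpretation. A randomized Day 1-3 difference remains valid, and Day 30 is unaffected. What is lost is the ability to assign a Day 1-3 result, above all a null, to an acute or a residual effect. The size of any dilution is unknown and is not estimated here. Confidence is high on the texts and lower on the practical effect. The matter should be corrected, but it does not undermine the trial.

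**What to change.** 1. In section 7.3.2, limit the Visit 3 pill to the 14-day group as that day's scheduled pill, and state that group 1 receives only the 2-hour pill. Add a 2-hour column to the table in section 7.1.1 and move randomization and dispensing into it, to match sections 4.1, 6.1.5 and 10.1 and Visit 2.
2. For the 14-day group (about 50 athletes and 40 controls), set one scan-day dosing rule, the same in both arms, covering ASL and BOLD. Either scan before that day's pill, or scan at a fixed interval after it with symptom and cognitive tests done first. The order matters under the second option: Table 4 in section 8.2.2 shows headache in 16% versus 4% and flushing in 10% versus 1%, which could colour symptom scores or hint at allocation. State which drug state Day 1-3 represents.
3. Record time of last pill and time of scan in the database for each follow-up scan.

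The cost is text corrections, slightly less scheduling freedom in the 14-day group, and two extra fields for about (100 + 80) × 2 = 360 scans. The diary already asks when the drug was taken.

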#### Follow-up Visit (Visit 4, Day 30)

- Symptom questionnaire
- Collect blood/saliva for biochemistry, biomarker testing
- MRI procedures
- Neuropsychological testing

## Follow-up Visit (Visit 5 [Phone Visit], Day 14 after completion of the study)

- Symptom questionnaire
- Safety Assessment

## 7.3.3 EARLY TERMINATION VISIT

If the study is terminated early, the final visit would consist of collecting a blood/saliva sample and administering the neuropsychological testing and symptom questionnaire (at time-

points after day 10 after injury). The MRI scan would also be necessary in cases where the study ends after the 10-day post-enrollment.

#### 7.4 JUSTIFICATION FOR SENSITIVE PROCEDURES

In this study, placebo will be used as a comparator to assess whether sildenafil improves CBF, potentiates CVR, reduces symptoms, and improves cognitive outcomes in the brain injured athletes.

## 7.5 CONCOMITANT MEDICATIONS, TREATMENTS, AND PROCEDURES

#### 7.5.1 PRECAUTIONARY MEDICATIONS, TREATMENTS, AND PROCEDURES

1. Sildenafil is contraindicated for use in people that are hypersensitive to any component of the tablet.

2. Sildenafil has a systemic effect vasodilatory effects, which may be augment the effect of other anti-hypertensive agents.

3. Caution should be used when using Viagra and ritonavir, since concomitant administration of the protease inhibitor, ritonavir, substantially increases serum concentrations of sildenafil.

4. Caution is advised when Phosphodiesterase Type 5 (PDE5) inhibitors are coadministered with alpha-blockers.

5. Combinations of Viagra with other erectile dysfunction medications (Revatio) is not recommended.

6. Sildenafil use is contraindicated with regular and/or intermittent use of organic nitrates.

7. Sildenafil should not be taken with other PDE5 inhibitors.

8. Co-administration of Cimetidine (800mg), erythromycin, or saquinavir with sildenafil is cautioned since a combination of any of these drugs with sildenafil results in a great increase in sildenafil systemic exposure.

## 7.6 RESCUE MEDICATIONS, TREATMENTS, AND PROCEDURES

In cases of overdose, standard supportive measures should be adopted as required. Renal dialysis is not expected to accelerate clearance as sildenafil is highly bound to plasma proteins and it is not eliminated in the urine.

## 7.7 PARTICIPANT ACCESS TO STUDY AGENT AT STUDY CLOSURE

Protocol UT-7529 N/A

## 8 ASSESSMENT OF SAFETY

#### 8.1 SPECIFICATION OF SAFETY PARAMETERS

Adverse events will be reported in accordance with Federal NIH requirements. All adverse events, serious and non-serious, expected and unexpected, related and unrelated will be tracked by the study coordinator.

Serious or unexpected adverse events and other unanticipated problems will be reported orally as soon as possible and in writing within 7 days if life-threatening and within 15 days otherwise. Expected or non-serious adverse events will be reported at the time of continuing review.

## 8.1.1 DEFINITION OF ADVERSE EVENTS (AE)

Adverse event means any untoward medical occurrence associated with the use of an intervention in humans, whether or not considered intervention-related.

## 8.1.2 DEFINITION OF SERIOUS ADVERSE EVENTS (SAE)

An AE or suspected adverse reaction is considered "serious" if, in the view of either the investigator or sponsor, it results in any of the following outcomes: death, a life-threatening adverse event, inpatient hospitalization or prolongation of existing hospitalization, a persistent or significant incapacity or substantial disruption of the ability to conduct normal life functions, or a congenital anomaly/birth defect. Important medical events that may not result in death, be life-threatening, or require hospitalization may be considered serious when, based upon appropriate medical judgment, they may jeopardize the patient or subject and may require medical or surgical intervention to prevent one of the outcomes listed in this definition.

## 8.1.3 DEFINITION OF UNANTICIPATED PROBLEMS (UP)

Unanticipated problems involving risks to participants or others to include, in general, any incident, experience, or outcome that meets all of the following criteria:

• Unexpected in terms of nature, severity, or frequency given (a) the research procedures that are described in the protocol-related documents, such as the IRB-approved research protocol and informed consent document; and (b) the characteristics of the participant population being studied;

• Related or possibly related to participation in the research ("possibly related" means there is a reasonable possibility that the incident, experience, or outcome may have been caused by the procedures involved in the research); and

• Suggests that the research places participants or others at a greater risk of harm (including physical, psychological, economic, or social harm) than was previously known or recognized.

